## **5.4 Selection and Timing of Dose for Each Subject**

Patients will be randomized in a 1:1 scheme to receive abatacept at recommended dosing or placebo. The recommended dosage is 125 mg/mL single-dose prefilled glass syringe for subcutaneous injection. Patients will give themselves the first injection in clinic under the supervision of the study nurse and will self-inject at home thereafter on a weekly basis. If desired a family member can give the injection but must come to the clinic to be supervised by the nurse at the first dose.

### **5.4.1 Dose Modifications**

Immune suppressants will be stopped on or before baseline. Patients will be encouraged to taper any daily oral steroids as tolerated, if and when they begin to improve. Dose increases of oral steroids will not be allowed. No specific changes in dosing of abatacept are part of the protocol, however study medication may be held for one visit once (maximum) during the first 6 months in the protocol due to medical decision or extenuating circumstances, however open label study medication can be withheld at any time at the discretion of the investigator.

## **5.5 Blinding/Unblinding**

Blinding is critical to the integrity of this clinical study. However, in the event of a medical emergency or pregnancy in a subject, in which knowledge of the investigational product is critical to the subject's management, the blind for that subject may be broken. Before breaking the blind of an individual subject's treatment, the investigator should have determined that the information is necessary, ie, that it will alter the subject's immediate management. In many cases, particularly when the emergency is not investigational product-related, the problem may be properly managed by assuming that the

subject is receiving active product without the need for unblinding. The BMS Bioanalytical Science representatives and contract resource organizations performing the testing will be unblinded to the randomized treatment assignments in order to minimize unnecessary analysis of PK and immunogenicity samples from the placebo group of subjects.

## **5.6 Concomitant Treatments**

### **5.6.1 Prohibited and/or Restricted Treatments**

See Exclusion Criteria for limitations to treatments that may have been taken prior to entry into the protocol. During the protocol, immune suppressants will be withdrawn at or before the baseline visit (with optional steroid rescue therapy as described in the main body of the protocol) and will not be restarted unless the patient flares at or after Month 3 or earlier to a degree that the protocol-allowed steroid injection is not considered appropriate. Initiation of immune suppressant medication at that point would not be considered a protocol violation, but may dictate non-responder status during the rest of the trial. However, should a patient develop a degree of flare which, in the opinion of the investigator is inappropriate for continuing the protocol, this will be counted as non-response and the patient must be withdrawn from the protocol and study treatment stopped.

### **5.6.2 Other Restrictions and Precautions**

SLE is a complicated disease and it is sometimes difficult to determine if acute illness is caused by infection, lupus disease, or medication side effects. For this reason, supervision of the study clinic by a physician experienced in the care of lupus patients is imperative. Five such physicians will be available to follow the patients in this study, Drs. [name], [name], [name], , [name] and [name], as well as [name], DNP, APRN. Adverse events will be reported to the IRB and reviewed by the DSMB as described elsewhere in this protocol.

## **5.7 Treatment Compliance**

After the first injection, patients will self-administer injections at home and will keep a diary to record date and time of each injection. They will be asked to return the used syringes to the clinic at each

visit. They will be questioned at each visit about problems with administration and/or degree of compliance that has been possible. These records will be kept as part of the study records so that overall compliance in the treatment vs placebo group can be estimated.

## **6. STUDY ASSESSMENTS AND PROCEDURES**

### **6.1 Time and Events Schedule**

Qualified subjects who meet screening criteria will return to the clinic within one month for randomization (Treatment Visit 1). Because study treatments are weekly, window for dosing shall be  $\pm 3$  days.

All visits include sufficient history, physical examination, and diagnostic testing to meet the requirements for scoring the SLEDAI and BILAG. Because of this they are all adequate for performing a complete safety and well-being assessment. Therefore no specific new procedures will be specified for either end of study or safety follow up visits. Interim visits for adverse events will be performed as clinically warranted. The reason for any early withdrawal/study drug discontinuation will be documented. Patients are referred to our research cohort from throughout Oklahoma and surrounding states.

**TIME AND EVENTS SCHEDULE: PROTOCOL IM101-345**

Procedure	Screening Visit	Treatment Visit 1 1 st Dosing	Treatment Visit 2-7 Month 1-6	Follow up Visits post-Rx	Visits 8-13 Month 7-12
Eligibility Assessments					
Informed Consent	X*				
Inclusion/Exclusion Criteria	X	X			
Medical History	X	X	X	X	X
Safety Assessments					
Medication List	X	X	X	X	X
History, Vital Signs, Physical Examination	X	X	X	X	X
Adverse Events Assessment		X	X	X	X
Clinical Laboratory Tests	X	X	X	X	X
PK sampling	X**	X**	X**		X**
Immunogenicity	X***	X***	X***		X***
PD sampling	X****	X****	X****		X****
Pregnancy Test	X	X	X	X	X
Efficacy Assessments					
SLEDAI/SSFI/PGA	X	X	X	X	X
BILAG 2004	X	X	X	X	X
CLASI	X	X	X	X	X
DIAL	X	X	X	X	X
Patient Questionnaires (SF-36, LupusPRO)	X	X	X	X	X
Clinical Drug Supplies					
Randomize		X			
Dispense Study Treatment baseline and q month		X	X		X

\*Repeated for protocol amendments or new safety data

\*\* Screening, Months 1,2, 3,4, 6, 7,8, and 12 and/or EOS (if patients withdraw early)

\*\*\*Screening, Months 1,2, 6, 7, 8, 12 and/or EOS

\*\*\*\* At Screening Visit, first dosing, visits 3, 6, 9 and 12 and/or EOS (</= 160 cc blood, up to 30cc urine, up to 10cc saliva)

Non PD visits are restricted to </= 80 cc blood, up to 30 cc urine, up to 10 cc saliva)

Note that PK/PI/PD labs at screening should be drawn at the screening visit if possible, otherwise may be drawn anytime up to and including the First Dosing Visit, but must be draw prior to receiving any steroid injection(s) in the protocol.

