Subjects will be encouraged to avoid off protocol medications if possible, but if off protocol medications are given, the patient may, at the discretion of the investigator continue in the protocol as a designated “non-responder”, and continue to be followed at monthly visits until the subjects reaches Month 6. Furthermore, patients may elect to receive open label abatacept as early as Month 3 (three Months after the first Dosing Visit) if their disease activity is not improved at that visit compared to baseline. Such subjects will also be designated as non-responders for the primary endpoint at Month 6. For those patients taking daily oral steroids at screening, they will be encouraged to taper these as tolerated if and when they begin to improve. Patients who withdraw from the protocol for any reason will be encouraged to come for safety follow up visits 2 and 4 months after the last study visit.

The primary endpoint will be determined at six months, but all patients can then choose to receive open label abatacept for an additional six months. Maximal duration of treatment will be 12 months. There will be two follow up visits two and four months after the end of study. However, patients who withdraw after six months will be considered completers of the primary study in the amassing of 60 completers. The criteria for evaluation will be improvement (without worsening) in signs, symptoms and diagnostic results as defined by the BICLA (primary endpoint). Additionally joint counts, the SRI 4/5, hybrid SLEDAI, BILAG 2004, CLASI, DIAL, Lupus PRO and SF-36 will be evaluated.

After receiving the first injection in clinic, patients will administer the study medication at home. Subjects will return to the clinic monthly for six months, and those who continue will be evaluated every 4 weeks for the second six months. There will be two follow up visits at two month intervals after the end of study for each patient. Visits at which maximal blood samples are taken due to PD scheduling are Screening, and Months 3, 6, 9 and 12 (up to 160 cc). At all other visits no more than 80 cc maximally can be drawn.

Please refer to the Time and Events Schedule for a grid of procedures.

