**Primary Biologic Endpoint (Which is a secondary endpoint for the trial):**

To test the applicability of baseline imbalance in a.) relative differences in the ratio of *IL6/IL23/IL17* to *Foxp3/TGFβ* (suggesting T Cell signaling imbalance) OR an elevated B cell activation profile to predict clinical response to abatacept either through pre-dose elevation or post-dose reversal of this profile. Based on considerations reviewed in the preliminary data section, the primary biomarker for T

Cell signaling imbalances will be gene expression levels of *IL6/IL23/IL17* and *Foxp3/TGFβ*. The primary biomarker for T Cell signaling-induced B Cell signaling imbalance will be ERK

phosphorylation after cognate interactions between T Cells and the B cell receptor as has been described above.

This will require 8 ml of blood for several cellular response/ stimulation experiments. Follow up samples will be drawn at Month 3 prior to “non-responders” starting new immune suppressant medications, which could confound later biologic assays. This will be repeated at Month 9 to include changes in placebo-treated patients after 3 months on abatacept **respecified Secondary Biologic Analyses**

1. Circulating cytokines of interest (Baseline Month 3 and Month 9) The cytokines to be measured are more easily detected in plasma than in serum. Our Serum Analyte and Biomarker Core has expanded extensive effort in optimizing a 51-plex cytokine assay which is based upon the

BioRad200 platform. Preliminary data from this approach is presented above. This will allow direct testing of select hypotheses, such as abatacept effects on IL-6, IFN alpha, BLyS and TNFRI/II pathways, but also in providing a more exploratory analysis of additional cytokines and chemokines important in T and B cell activation. This method uses a two laser immunobead multiplex technology allowing the levels of 51 cytokines to be monitored with a only 5-8 ml of blood. Serum levels of BLyS and APRIL will also be tested but are unable to be multiplexed based upon features of those analytes.

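### The PD footnote of the Time and Events Schedule lists visit numbers that its own grid maps to Months 2, 5, 8 and 11, while the rest of the protocol places PD samples at Months 3, 6, 9 and 12

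*Combined protocol and SAP*

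**What the plan says.** Section 6.1 has eligible subjects "return to the clinic within one month for randomization (Treatment Visit 1"), so Visit 1 is the first dosing visit. The grid's next treatment columns are headed "Treatment Visit 2-7 Month 1-6" and "Visits 8-13 Month 7-12".

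The footnotes to that grid do not share one unit. The PK footnote counts in months: "Screening, Months 1,2, 3,4, 6, 7,8, and 12 and/or EOS (if patients withdraw early"). The immunogenicity footnote also uses months. The PD footnote counts in visits: "At Screening Visit, first dosing, visits 3, 6, 9 and 12 and/or EOS". A further note, beginning "Non PD visits are restricted to", sets the 80 cc blood limit for every visit not listed for PD; listed visits may go to 160 cc.

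Elsewhere PD timing is given in months:

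- Section 4.1: "Visits at which maximal blood samples are taken due to PD scheduling are Screening, and Months 3, 6, 9 and 12".
- Section 6.4.2, Primary Biologic Endpoint: "Follow up samples will be drawn at Month 3 prior to" non-responders starting new immune suppressants, with a repeat at Month 9 so that placebo patients have had three months of abatacept.
- Section 6.4.2, secondary biologic analyses, and the optional exploratory analyses that follow: mostly baseline, Month 3 and Month 9.
- Appendix 6: baseline and 3, 6, 9 and 12 months, or early termination.
- Appendix 3: baseline, 3 and 6 months and/or end of study, for the complement assay.
- Section 7.2.2, blood-draw paragraph: baseline, Month 3 and Month 6 as the major PD visits.

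**The concern.** Section 4.1 sends the reader to the grid for the procedures at each visit, so the footnote is an operative instruction. Visit numbers and months differ by one in this trial. Because the neighbouring footnotes use months, a careful reader has some reason to take the word visits at face value.

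The timing of the two key samples is deliberate. Month 3 was chosen to come before treatment changes that could confound later assays, and Month 9 to give placebo patients a fixed period on active drug. Section 9.4.4 compares response rates in patients whose TH17 signal has moved at least 50% towards normal after treatment. That part of the endpoint depends on when the follow-up sample is taken. The part that uses only the baseline profile does not.

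**Working it through.** **Inputs.** Visit 1 = first dosing = Month 0 (Section 6.1 and the grid). Visits 2-7 = Months 1-6: six visits, six months. Visits 8-13 = Months 7-12: six visits, six months.

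**Formula.** Month = visit number − 1, throughout Visits 1 to 13. The month scale counts from first dosing: the synopsis and Section 4.1 define Months 2 and 3 as two and three months after the first dosing visit, and Appendix 6 puts Month 2 at Day 57 and Month 3 at Day 85.

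| PD footnote | Month under the grid | Month in Section 4.1 and Appendix 6 | Visit for that month | Shift |
|---|---|---|---|---|
| Visit 3 | 3 − 1 = 2 | 3 | 3 + 1 = 4 | 1 month early |
| Visit 6 | 6 − 1 = 5 | 6 | 6 + 1 = 7 | 1 month early |
| Visit 9 | 9 − 1 = 8 | 9 | 9 + 1 = 10 | 1 month early |
| Visit 12 | 12 − 1 = 11 | 12 | 12 + 1 = 13 | 1 month early |

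The sets {2, 5, 8, 11} and {3, 6, 9, 12} have no month in common. For the first draw the shift is Day 85 − Day 57 = 28 days.

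**Consequences of the literal reading.**

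1. *Month 2 instead of Month 3.* Section 4.2.2, item 6(d), allows depomedrol from screening until the end of the Month 2 visit. A Month 2 draw lies inside that window; a Month 3 draw lies about a month after it closes.
2. *Month 8 instead of Month 9.* For a placebo patient who starts open-label drug at Month 6, exposure at sampling is 8 − 6 = 2 months, not 9 − 6 = 3 months.
3. *Month 5 instead of Month 6.* The draw no longer coincides with the primary BICLA assessment.
4. *Blood limits.* Visits 4, 7, 10 and 13 become non-PD visits, limited to 80 cc instead of 160 cc.

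**Related inconsistencies.** Section 7.2.2 limits blood to 120 cc at baseline, Month 3 and Month 6 and to 60 cc at all other visits. Section 4.1 and the grid give 160 cc and 80 cc. At Months 9 and 12 the limit is thus 60 cc in Section 7.2.2 and 160 cc in Section 4.1. Section 5.1 ties the depomedrol total to Visit 2, which the grid makes Month 1 (2 − 1), while the same paragraph permits injections at Months 1 and/or 2 and the synopsis, Section 4.1 and Section 4.2.2 refer to the Month 2 visit.

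**The case against.** The best defence is that this is a wording slip. The footnote's numerals are exactly the PD months in Section 4.1 and Appendix 6, and Month 3 or Month 9 is repeated across Section 6.4.2, Section 7.2.2 and Appendix 3. No text gives Month 2, 5, 8 or 11 as a PD time. Section 5.1 also mixes visit and month labels within one paragraph. This stands: the intended timing is hardly in doubt. It does not remove the contradiction in the operative schedule.

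A reader might infer more than the documents support:

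- *That the Month 3 and Month 9 samples will be lost.* This happens only if staff apply the grid's numbering against the other sections. Even then four post-baseline draws remain; they are moved, not dropped. The 80 cc limit would not block the 8 ml that the primary biologic endpoint needs, although the grid would not call for it. The end-of-study clause might also recover a Month 6 or Month 12 draw for patients who stop then.
- *That no pre-switch sample would exist.* Open-label drug starts no earlier than Month 3 (Section 4.1) or Month 4 (Section 5.3), so a Month 2 sample is also pre-switch. It is early, not absent.
- *That both samples are at risk in all 60 patients.* The second six months are optional (Section 4.2.3), so Month 9 exists only for those who continue.
- *That Section 6.4.2 needs all four months.* It names Months 3 and 9, apart from immunoglobulin at all visits. Months 6 and 12 come from Section 4.1 and Appendix 6.

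The depomedrol argument also has a limit. Item 6(d) has blood drawn before any injection at the Month 2 visit itself, so the contamination risk comes from earlier injections. If these were given only at the visits listed in Section 5.1, the latest would be about a month old. They could be more recent only under the any-time wording of item 6(d).

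**Conclusion.** The inconsistency is real and rests on the grid's column headings alone. Read literally, the PD footnote puts every scheduled post-baseline PD draw one month before the time given in Section 4.1 and Appendix 6, and includes neither follow-up time of the primary biologic endpoint. It is probably a slip for months, so mistimed sampling is a risk and not an expected outcome.

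If the risk materialised, the effect would be confined to biologic endpoints that are secondary or exploratory and, for the primary biologic endpoint, described with confidence intervals. The Month 9 part would concern only extension patients, and the figure of two rather than three months applies to placebo patients who switch at Month 6. The primary BICLA comparison and the power calculation do not use PD samples and are unaffected. The correction should still be made, because a draw taken at the wrong visit cannot be retaken at the right one.

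**What to change.** 1. Change the PD footnote to Months 3, 6, 9 and 12 (Visits 4, 7, 10 and 13). Giving both labels removes the ambiguity and puts the footnote in the same unit as the PK and immunogenicity footnotes.
2. Reconcile the PD visit list and blood-volume limits in Section 7.2.2 with Section 4.1 and the grid, so that one list and one set of limits apply.
3. Reconcile the Visit 2 wording in Section 5.1 with the Month 2 wording in the synopsis, Section 4.1 and Section 4.2.2. Which limit is meant is for the sponsor and investigator to state; this review proposes none.

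The first change is one line. The other two are short text corrections that can go into the same amendment. None adds a visit, a procedure or an analysis. If sampling has already begun, record the actual date of each PD draw and analyse by actual time since first dose.

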## **6.2 Study Materials**

Bristol-Myers Squibb (BMS) will provide abatacept subcutaneous formulation at no cost for this study.

**6.3 Safety Assessments** All subjects who receive a dose of abatacept will be evaluated for safety. Safety outcomes include adverse events, clinically significant changes in vital signs, laboratory test abnormalities, and tolerability of the drug. The investigator will determine the severity of each adverse event as mild, moderate, severe, or very severe. Reference will be made to the National Cancer Institute Common Terminology Criteria for Adverse Events. Laboratory findings that the investigator rates as clinically significant will be recorded as adverse events. The investigator will determine the relationship of the adverse event to the study drug. Any occurrence of a SAE from time of consent forward, up to and including follow-up visits will be reported. See Section 7.3.1 for the SAE reporting procedures.

### **6.3.1 Physical Examinations**

Physical examinations will be performed at every visit, suitable to assess patient safety and to perform the efficacy evaluations which are multisystem indices (see below)

### **6.3.2 Breast and Hematologic Cancer Screening**

Patients with SLE have a slightly decreased risk for breast cancer compared to healthy controls and a slightly increased risk for lymphoma. Appropriate general cancer screening procedures will be discussed with each patient entering the study. Female subjects who are greater than 50 years of age will have a manual breast examination performed at the screening visit and all subjects will be examined for lymphadenopathy. Subjects having a cancer screening that is suspicious for malignancy will have drug administration withheld until the possibility of malignancy can be reasonably excluded following additional clinical, laboratory or other diagnostic evaluations. The screening period may be extended under such circumstances at the discretion of the investigator.

## **6.4 Efficacy Assessments**

The efficacy assessments that have been documented in the Time and Events Schedule are described below. Case report forms are included in the Appendices.

### **6.4.1 Primary Efficacy Assessment: BICLA Response**

BICLA stands for BILAG-based Combined Lupus Assessment. The BILAG refers to the British Isles Lupus Assessment Group Index. We will be using the version known as BILAG 2004 (37). This consists of 97 descriptors for signs and symptoms of lupus divided into 9 organ systems (see appendices for case report forms). Each organ system receives a rating of A (severe disease activity), B (moderate disease activity) C (mild disease activity) D (no disease activity in an organ previously affected) or E (organ inactive and never previously active). These ratings are derived from assessments made on each descriptor within each organ and the determination of whether activity is not present, improving, same, worsening or new/recurrent when comparing the degree of disease activity during the past month to the previous month.

The BICLA (8) includes scores from the BILAG, the SLEDAI and the PGA. The SLEDAI which will be used is the hybrid SLEDAI which incorporates components of two SLEDAI versions, the SLEDAI 2K and the SELENA SLEDAI which was devised for the Safety of Estrogens in Lupus Erythematosus

National Assessment (SELENA) trial. The PGA refers to Physician's Global Assessment which is performed on a weighted 100 mm scale devised specifically for lupus designed as part of the SLEFI (SELENA SLEDAI flare index). Based on the BILAG scores at entry (A-E in each organ) the BICLA response is defined by at least one letter grade improvement in each organ without an increase in the SLEDAI score or an increase of 10% in the PGA. There must also be no off-protocol treatment in order to meet this response criteria. The primary endpoint is BICLA response rates at month 6 in the abatacept treatment group vs the placebo group. BICLA response at each month will also be assessed as a secondary endpoint.

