## 4 INVESTIGATIONAL PLAN

### 4.1 Study Design and Duration

**Planned Study Design:** This will be a randomized, double blind, placebo-controlled trial of patients with active SLE who must have active arthritis (at least BILAG B and at least 3 tender and 3 swollen joints) at the screening visit. Randomization to placebo vs abatacept will be performed on a 1:1 scheme by an unblinded pharmacy technician who will have no contact with study subjects. Patients will give weekly subcutaneous injections of study drug at home except for the first dose which they will give in clinic under the supervision of a nurse/coordinator.

Subjects will be evaluated monthly by an investigator/subinvestigator who are required to have passed LFA testing for Hybrid SLEDAI, BILAG 2004 and CLASI. Additional assays will be PROs (Lupus PRO and SF36) and the DIAL endpoint (endpoints are defined below and case report forms for each endpoint can be found in Appendices). The primary endpoint will be measured at 6 months. This will be a comparison of response rates by the BICLA (BILAG-based Combined Lupus Assessment) which is a scoring system incorporating several measures. Improvement must be documented using the BILAG (British Isles Lupus Assessment Group) index, with no worsening in any organ by BILAG or SLEDAI (SLE Disease Activity Index) and less than 10% worsening in PGA (Physicians Global Assessment) as well as no initiation of off protocol immune suppressants or steroids.

Secondary endpoints will include changes in each of the above mentioned single outcome measures, CLASI, and assessment of patient reported outcomes (secondary endpoints are further described below). Biomarker evaluations with a specific focus on T Cell subset pathways and B Cell pathways will also be explored in a responder analysis.

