## **6.4.2 Secondary Efficacy Assessments**

***All of the individual components of the BICLA will be assessed in different ways as secondary endpoints. These will include:***

1. BICLA response at each month
2. SRI 4 and 5: Response is defined at an endpoint date (EOS and each month vs baseline) The SRI endpoint (7) is defined as a 4 (or 5) point drop in SLEDAI compared to baseline without an increase in BILAG or 10% worsening by PGA.
3. Tender and swollen joint counts (to be analyzed separately and as composite score)
4. Change in SLEDAI scores (EOS and each month vs baseline)
5. Change in PGA scores (EOS and each month vs baseline)
6. Change in BILAG numerical scores (Addition of organ scores where each A=12, B=8, C=1 and D or E=0).
7. Musculoskeletal BILAG response (% with one grade drop and % who reach C or lower)
8. Responder Analysis using the primary endpoint and assessing baseline evidence of (and changes in) a panel of markers selected to identify high levels of IL6/TH17 signalling, and/or B Cell signaling (Erk/Blys). All methods proposed have been previously standardized and are currently available in our laboratory as reviewed above. These will be re-standardized for the current study.

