### 9.2 Populations for Analyses

**The subject population** As further detailed in the inclusion and exclusion criteria will consist of consecutive consenting lupus patients between ages 18 and 70 who have active polyarticular arthritis characterized by 3 or more tender and 3 or more swollen joints at the screening visit meeting the BILAG 2004 criteria for  $\geq$  B disease (+/- additional evidence of disease activity in other organs).

**The clinical justification** is based on the combination of unmet need in treating a significant, potentially disabling illness, while ensuring a healthy enough population to justify the risks of studying a biologic treatment vs placebo.

**Power Analysis:** Chi Sq or the Fisher's exact test will be used for analysis. The table below has been powered on the assumption that the placebo group will have a result similar to (or even a bit more responsive than) that found in the BOLD study (which was the test prototype for this protocol to determine the safety and feasibility of the statistical assumptions for the placebo study). Data from the BOLD study confirm that there should be a near zero (2.4%) percent response by BICLA at six months in the placebo group in a study with background IS withdrawal. Therefore our assumption of at least 5% response in the placebo group in an identical trial design is reasonable. The second assumption is that the treatment group will have a response rate somewhere between those found in the epratuzumab (by BICLA) and BLISS phase II/III (by SRI) biologic studies e.g. a predicted response rate between 35 and 50%. The most important basis for this assumption, however are the data from patients with lupus arthritis in the Phase II abatacept study, where physicians rated 40% of

the patients treated with abatacept as having “no flare” after baseline. Therefore this expected range by BICLA seems reasonable. (please see power analysis table below which is based on powering the primary endpoint at a range of expected response rates in treatment and placebo groups with a sample size of 60 patients, alpha=0.05).

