#### **9.3.2 Secondary and Exploratory Endpoint Definitions** (see specific descriptions of endpoints in 6.41 and 6.42, below some further discussion of the analysis plan

### **9.4 Analyses To Be Performed**

#### **9.4.1 Demographics and Baseline Characteristics**

The demographics of the patients who are likely to participate in this study should be reflective of the Oklahoma Lupus Cohort which will be the source for most of our recruitment activity. The age range of participants in this study will be between 18 and 70, and based on our experience with interventional trials requiring significant disease activity, we expect the majority of subjects to be within the ages of 25 and 55. There is no stratification scheme to be imposed based on demographics and baseline characteristics, but variables of age, race, gender, steroid use, autoantibody positivity, complement consumption, and BILAG score at baseline will be described in order to identify any glaring imbalances in group assignments..

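### Sections 4.1 and 6.4.1 give different rules for BICLA response, the only powered endpoint, and the rule in 6.4.1 cannot be met by a patient with an inactive organ system

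*Combined protocol and SAP*

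**What the plan says.** Section 6.4.1 grades nine BILAG systems A to E. D is inactive but previously affected, and the last grade is "E (organ inactive and never previously active". It then states that "the BICLA response is defined by at least one letter grade improvement in each organ without an increase in the SLEDAI score", adds a 10% limit on PGA increase, and bars off-protocol treatment. It does not restrict the rule to organs active at entry and has no separate condition against BILAG worsening.

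Section 4.1 describes the same endpoint differently. BILAG improvement must be documented, with no size and no every-organ requirement, "with no worsening in any organ by BILAG or SLEDAI (SLE Disease Activity Index) and less than 10% worsening in PGA", and with no off-protocol immune suppressants or steroids. Later, 4.1 summarises the criterion as "improvement (without worsening) in signs, symptoms and diagnostic results as defined by the BICLA (primary endpoint".

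Nothing else settles the difference. Sections 9 and 9.4.3 and the synopsis name BICLA without defining it. Section 9.3.2, headed for secondary and exploratory endpoints, only points back: "see specific descriptions of endpoints in 6.41 and 6.42". For eligibility, Sections 4.1 and 4.2.1 require active arthritis, and Section 9.2 makes "additional evidence of disease activity in other organs" optional.

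**The concern.** Sections 2.1 and 9.4.3 say that the study is powered on this one responder comparison, so the responder rule has to give one answer per patient. Taken literally, 6.4.1 asks for something most of the eligible population cannot achieve. Taken in the obvious workable way, it drops a safeguard that 4.1 states. The omission is not a habit of Section 6.4: the secondary SRI in 6.4.2 is defined as a "point drop in SLEDAI compared to baseline without an increase in BILAG or 10% worsening by PGA", so the BILAG condition is present for the secondary index and absent for the primary one.

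With 30 patients per arm and 5% assumed on placebo, about 30 × 0.05 = 1.5 placebo responders are expected, so single classifications count. An unsettled rule also leaves room to choose a reading after results are known.

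**Working it through.** **The plan's own figures.** 1/41 = 2.4%, as Section 9.1 states for BOLD. For 40% v 5%, 30 per arm and alpha 0.05 (two-sided assumed), the continuity-corrected normal formula is power = Φ[(|p1−p2| − 1/n − 1.96·SE0)/SE1]. SE0 = √(2 × 0.225 × 0.775/30) = 0.1078 and SE1 = √((0.40 × 0.60 + 0.05 × 0.95)/30) = 0.0979. This gives Φ[(0.35 − 0.0333 − 0.2113)/0.0979] = Φ(1.076) = 0.859, against 0.86 in the power table. The table's arithmetic for this column is not in dispute. The question is which patients count as responders.

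**The literal rule.** D cannot become E, because E means never active, and E has nothing below it. A patient can therefore respond only if all nine systems are at A, B or C at entry and all nine improve. Section 4.2.1 requires activity in one system.

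**Three patients scored by each section.** The inputs are Appendix 2 (a new mild skin eruption makes mucocutaneous B; a musculoskeletal B feature recorded as improving becomes C) and Appendix 1 (arthritis 4 points, rash 2). All other systems are D or E throughout, PGA is unchanged and there is no off-protocol treatment.

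| Patient | Entry | Month 6 | SLEDAI | 6.4.1 literal | 6.4.1, active organs only | 4.1 |
|---|---|---|---|---|---|---|
| 1 | Musculoskeletal B, mucocutaneous D or E | D, B (new mild rash) | 4+0=4 to 0+2=2 | No | **Yes** | **No** |
| 2 | Musculoskeletal B, mucocutaneous B (rash) | C, B | 4+2=6 to 2 or 6 | No | **No** | **Yes** |
| 3 | Musculoskeletal B, mucocutaneous D | C, D | 4 to 0 or 4 | **No** | Yes | **Yes** |

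Patient 1 worsens by BILAG in the skin, which 4.1 forbids and 6.4.1 does not mention. Patient 2 improves in one organ and worsens in none, which satisfies 4.1, but one active organ has not improved. Patient 3 shows the literal rule failing a patient whom both other readings accept.

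The numerical BILAG in 6.4.2 ("Addition of organ scores where each A=12, B=8, C=1 and D or E=0") shows how far apart these are. Patient 1, a responder under 6.4.1, goes 8+0=8 to 0+8=8. Patient 2, a non-responder under 6.4.1, goes 8+8=16 to 1+8=9.

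**Points left open rather than contradicted.**
- Grade C: arthritis B to C with lymphocytes 0.9 at both visits keeps the haematological system at C and leaves SLEDAI unaffected. The patient responds only if a C system need not improve.
- PGA: a rise from 1.5 to 1.7 is 0.2/1.5 = 13.3% of the patient's value but 0.2/3 = 6.7% of the 0–3 scale in Appendix 1.
- SLEDAI: 6.4.1 reads as the total score, while 4.1 can be read as organ by organ.

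**The case against.** The best reply is that 4.1 and 6.4.1 describe one endpoint and should be applied together: 4.1 supplies the safeguard, 6.4.1 the size of improvement, and neither cancels the other. The summary in 4.1 of improvement without worsening supports this. BICLA is also a cited index, 4.1 requires assessors to have passed testing on its BILAG and SLEDAI components, and no trained scorer would demand improvement from an organ that was never active.

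Much of this stands as a guide to intent. Applying both conditions would make patients 1 and 2 non-responders. But no text says that the conditions are cumulative or that the cited source prevails over the written rule. Combining them also does not repair the every-organ wording: patient 3 still fails, and the entry grades that must improve remain unnamed.

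Two stronger readings are tempting. A reader might infer that both planning rates depend on matching a BICLA scoring rule. Only the placebo figure was obtained by BICLA in this design. Section 9.2 draws 35–50% on abatacept from epratuzumab (by BICLA), BLISS (by SRI) and, chiefly, a physician rating of no flare in 40% of abatacept-treated arthritis patients. No single scoring rule lies behind it.

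A reader might also infer a loss of power. If 10% of responders in both arms were reclassified (36% v 4.5%), the formula above gives 0.794, just under the 0.80 target. That share is purely an assumption, and the documents give no frequency from which to estimate it.

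**Conclusion.** The point stands as an inconsistency in the definition of the primary endpoint. Read literally, 6.4.1 makes any patient with one D or E system a non-responder. That is plainly not intended, given a BICLA responder in BOLD and entry criteria that require only arthritis, but 6.4.1 states no alternative. Under the workable reading, which is itself an inference, 6.4.1 and 4.1 classify some patients differently, in both directions. Grade C, the base of the PGA percentage and total versus by-organ SLEDAI are under-specified and lesser matters; the two PGA conditions agree in substance. The size of the effect on response rates or power cannot be derived from the documents and none is claimed. The point needs correcting before unblinding because it concerns the only powered endpoint and the correction is cheap.

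**What to change.** Before unblinding, place one identical BICLA definition in 4.1 and 6.4.1, with the synopsis referring to it. It should:

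- replace the every-organ requirement with each system at named active entry grades, confirmed against the cited BICLA source and the scoring that gave 1/41 in BOLD, which also settles grade C;
- carry over from 4.1 the condition of no BILAG worsening in all other systems;
- say whether SLEDAI worsening is judged on the total or by organ, and what the PGA 10% is a percentage of.

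If the reference visit is fixed in the same edit, also state how a patient with no system left at the required grades on that visit is scored. BILAG B is required only at screening, randomization may follow up to a month later (Section 6.1), and steroid injections are permitted from screening, so such patients can arise.

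The cost is wording in two sections, a cross-reference, and a check of the BOLD scoring. No visit or assessment is added: BILAG, SLEDAI and PGA are already scheduled at screening, first dosing and monthly. Only the placebo assumption needs checking against the final rule. If BOLD was scored differently, restate that rate and the power that depends on it.
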